The age category immediately above the patient's exact age should be used. SDS is actually a Z score that measures the distance from the population mean in units of standard deviations. That is,  $SDS < 0$  refers to values lower than the population mean, and for example  $SDS \leq -1.645$  refers to values in the lowest 5%. (The usual percentile more commonly used in the clinical practice can be derived from the Z-score by a normal distribution).

The time-course of height and BMI SDS will be summarized, side by side, on the FAS of the studies CRAD001M2305 and TOSCA using descriptive statistics by year since the enrollment date (for TOSCA patients) or since the start of everolimus (for CRAD001M2305 patients). The counts and frequencies of patients with height and BMI SDS values lower than the 5th percentile (notably low) or higher than the 95th percentile (notably high) will be described on the FAS, overall and by region.

The rate of height (respectively BMI) growth notable abnormality will be calculated as the rate of patients with a height SDS  $<$  5th percentile at the last time point where height is reported.

If a high rate of notably height (respectively BMI) growth abnormality occurs in the CRAD001M2305 patients, the relationship between the everolimus exposure and the height growth abnormality will be further explored as detailed below:

- The rate of height (respectively BMI) growth abnormality will be described in the different subgroups defined by the duration of everolimus exposure. These subgroups will be defined in the Report and Analysis Plan.
- The duration of exposure and the age at start of everolimus will be summarized using descriptive statistics in the subgroups of patients with and without a height (respectively BMI) growth abnormality.
- A logistic regression including the duration of exposure and the age at the start of everolimus as continuous covariates will also be used to further explore the relationship between the everolimus exposure and the height (respectively BMI) growth notable abnormality. Additional covariates (e.g. time normalized Cmin) might also be included in the model.

In addition, individual patient graphs for height and BMI over time will be provided for CRAD001M2305 patients.

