The age category immediately above the patient's exact age should be used. SDS is actually a Z score that measures the distance from the population mean in units of standard deviations. That is, $SDS < 0$ refers to values lower than the population mean, and for example $SDS \leq -1.645$ refers to values in the lowest 5%. (The usual percentile more commonly used in the clinical practice can be derived from the Z-score by a normal distribution).

The time-course of height and BMI SDS will be summarized, side by side, on the FAS of the studies CRAD001M2305 and TOSCA using descriptive statistics by year since the enrollment date (for TOSCA patients) or since the start of everolimus (for CRAD001M2305 patients). The counts and frequencies of patients with height and BMI SDS values lower than the 5th percentile (notably low) or higher than the 95th percentile (notably high) will be described on the FAS, overall and by region. The counts and frequencies by region will be provided if sufficient sample size observed within the region for CRAD001M2305 study.

The rate of height (respectively BMI) growth notable abnormality will be calculated as the rate of patients with a height $SDS < 5$ th percentile at the last time point where height is reported.

If the number of CRAD001M2305 patients is sufficient and if a high rate of notably height (respectively BMI) growth abnormality occurs, the relationship between the everolimus exposure and the height growth abnormality will be further explored as detailed below:

- The rate of height (respectively BMI) growth abnormality will be described in the different subgroups defined by the duration of everolimus exposure. These subgroups are described in the Section 3.12.
- The duration of exposure and the age at start of everolimus will be summarized using descriptive statistics in the subgroups of patients with and without a height (respectively BMI) growth abnormality.
- A logistic regression including the duration of exposure and the age at the start of everolimus as continuous covariates will also be used to further explore the relationship between the everolimus exposure and the height (respectively BMI) growth notable abnormality. Additional covariates (e.g. time normalized Cmin) might also be included in the model.

In addition, individual patient graphs for height and BMI over time will be provided for CRAD001M2305 patients.

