3.13 Sample size calculation

No formal sample size calculation has been performed in this non-comparative study which consists in the long-term safety follow-up of CRAD001M2301 pediatric patients. It is anticipated that approximately 50 patients who have participated in CRAD001M2301 would be eligible to enter CRAD001M2305.

Based on the safety findings in Study CRAD001M2301 in terms of growth development where the estimated rate of patients with growth development abnormality was between 5 – 10% as of 11-Jan-2013 cutoff, it can be expected that the proportion of patients with growth development abnormality in this study would be in the same range, between 5 - 10%. The growth development abnormality would be defined as rate of notably low height SDS at the cut-off date of the analysis.

The proposed sample size of 50 patients will allow estimating a two-sided 95% confidence interval for rate of patients with growth development abnormality. [Table 3-1](#) below shows the exact binomial 95% confidence interval [[Clopper and Pearson 1934](#)] and the precision of the estimate for N=50 for various numbers of observed patients with growth abnormality. Note that the final interval will depend on the final sample size.

Table 3-1 95% confidence interval for different number of observed patients with growth development abnormality during CRAD001M2305 (sample size N = 50)

Number of patients with growth development abnormality	Rate of patients with growth development abnormality	Exact binomial 95% confidence interval
0	0.00	(0.00, 0.07)
2	0.04	(0.00, 0.14)
4	0.08	(0.02, 0.19)
6	0.12	(0.04, 0.24)
8	0.16	(0.07, 0.29)
10	0.20	(0.10, 0.34)
12	0.24	(0.13, 0.38)
14	0.28	(0.16, 0.42)

With this sample size of 50, if we observe 4 patients with growth development abnormality (which corresponds to an observed 8% rate) there will be 79% probability of true rate of patients with growth development abnormality $\leq 10\%$. Probabilities that the true rate of patients with growth development abnormality is lower or equal to 10% with different number of observed patients with development abnormality are illustrated in Table 3-2. These calculations are based on the binomial distribution.

Table 3-2 Probability that the true rate of patients with growth development abnormality is lower or equal to 0.10 as a function of number of observed patients with development abnormality

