4.2 Indirect Comparison Analysis

Confidence interval was so wide even for 1 patient with growth development abnormality as shown below in the table 1-1. Estimation was not robust due to the small sample size. Sample size of 15 patients is too small for any comparison, Considering the unlikelihood of making a robust analysis with the limited enrolment into CRAD001M2305, indirect comparison is not meaningful.

Table 1-1 95% confidence interval for different number of observed patients with growth development abnormality during M2305

Number of patients with growth development abnormality	Sample size N = 50		Sample size N = 15	
	Rate of patients with growth development abnormality	Exact binomial 95% confidence interval	Rate of patients with growth development abnormality	Exact binomial 95% confidence interval
0	0.00	(0.00, 0.07)	0.00	(0.00, 0.22)
1			0.07	(0.00, 0.32)
2	0.04	(0.00, 0.14)	0.13	(0.02, 0.40)
3			0.20	(0.04, 0.48)
4	0.08	(0.02, 0.19)	0.27	(0.08, 0.55)
5			0.33	(0.12, 0.62)
6	0.12	(0.04, 0.24)	0.40	(0.16, 0.68)
7			0.47	(0.21, 0.73)
8	0.16	(0.07, 0.29)	0.53	(0.27, 0.79)
9			0.60	(0.32, 0.84)
10	0.20	(0.10, 0.34)	0.67	(0.38, 0.88)
11			0.73	(0.45, 0.92)
12	0.24	(0.13, 0.38)	0.80	(0.52, 0.96)
13			0.87	(0.60, 0.98)
14				
	0.28	(0.16, 0.42)	0.93	(0.68, 0.998)

5 Appendix

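### Individual everolimus exposure is related to growth only through a yes/no outcome behind undefined conditions; with 15 patients that yields either no between-patient analysis or an uninterpretable one

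*SAP*

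**What the plan says.** Height and BMI SDS are calculated for each patient at each time point. The continuous values are summarised by year since the start of everolimus, side by side with the TOSCA patients, and individual height and BMI graphs are drawn. Both outputs are unconditional (SAP 3.8.1).

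The link to a patient's own exposure goes through a binary outcome. The rate of "growth notable abnormality will be calculated as the rate of patients with a height" SDS under the 5th percentile at the last reported time point is defined first, with BMI treated correspondingly. Three analyses then use it: rates by exposure-duration subgroup, exposure and age at start in patients with and without the abnormality, and a model: "A logistic regression including the duration of exposure and the age at the start of everolimus as continuous covariates will also be used". A third covariate is possible: "Additional covariates (e.g. time normalized Cmin) might also be included in the model".

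The whole block has a condition. Protocol 10.4.1.2 has one part: "If a high rate of notably height (respectively BMI) growth abnormality occurs in the CRAD001M2305 patients". The SAP has two: "If the number of CRAD001M2305 patients is sufficient and if a high rate of notably height (respectively BMI) growth abnormality occurs". Neither document gives a threshold.

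On numbers, SAP 3.13 still argues from the planned size ("The proposed sample size of 50 patients will allow estimating a two-sided 95% confidence interval") and from a 5-10% abnormality rate in the parent study, of which "it can be expected that the proportion of patients with growth development abnormality in this study would be in the same range". SAP 4.2 then says "Sample size of 15 patients is too small for any comparison" and uses this to drop the TOSCA indirect comparison. Section 4 does not mention the logistic regression.

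**The concern.** The stated primary objective is the effect of everolimus on height, BMI and sexual development. Whether children with longer exposure have lower SDS is a natural question within it. The plan holds a continuous measurement suited to that question, yet reduces it to an indicator that perhaps one patient in 15 will show.

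Both outcomes of the condition are unsatisfactory. If it is not met, no between-patient analysis of exposure and growth is reported. If it is met, a model with two or three covariates is fitted to a handful of events. Because the thresholds are unstated, the choice between these would be made after the data are seen.

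**Working it through.** **Inputs from the documents.** N = 15 (SAP 4.2); planned N about 50 and expected rate 5-10% (SAP 3.13); two covariates, possibly three (SAP 3.8.1). The 5-10% refers to low height SDS; no expected rate is given for BMI.

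**The plan's own figures.** The exact (Clopper-Pearson) limits in the SAP 4.2 table reproduce for N = 15. For example, 1/15 gives (0.002, 0.319), printed (0.00, 0.32), and 4/15 gives (0.078, 0.551), printed (0.08, 0.55). No sample size or power is stated for the logistic model.

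**Expected events**, E = N × p, with binomial probabilities for N = 15:

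| Rate | E | P(0 events) | P(≤1) | P(≤2) |
|---|---|---|---|---|
| 5% | 0.75 | 0.46 | 0.83 | 0.96 |
| 10% | 1.5 | 0.21 | 0.55 | 0.82 |
| 20% | 3.0 | 0.04 | 0.17 | 0.40 |
| 30% | 4.5 | 0.005 | 0.04 | 0.13 |

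**Ceiling if the rate is high.** The smaller outcome class cannot exceed 7 of 15. That is at most 7/2 = 3.5 patients per covariate with two covariates, and 7/3 = 2.3 with three. At the planned N = 50 and 5-10%, 2.5 to 5 events were expected, or 1.25 to 2.5 per covariate, so the cut outcome was already weak by design.

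**Information kept by the cut.** For a normal variable cut at proportion p, the fraction kept is φ(z)²/[p(1−p)].
- p = 0.05: 0.1031²/0.0475 = 0.224, so 15 patients count as about 3.4.
- p = 0.10: 0.1755²/0.09 = 0.342, so 15 patients count as about 5.1.

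**Behaviour of the logistic fit** (simulation, N = 15). Assumptions: normal SDS, one value per patient, correlation −0.5 between duration and age at start, true partial correlation about 0.5 between duration and SDS.
- No events or separation, hence no finite estimate: about 74%, 52%, 22% and 12% of data sets at rates of 5%, 10%, 20% and 30%.
- Wald-test power: 0.01 or less at every one of these rates.
- A likelihood-ratio test is no rescue. With no true effect it rejects in 14.5% of data sets at a 10% rate and 10% at a 30% rate, against a nominal 5%.

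**What a continuous model can do at N = 15.** With duration and age at start in the model there are 15 − 3 = 12 degrees of freedom and t = 2.179. The slope's 95% CI half-width is approximately t × σ / [SD(duration) × √14 × √(1−ρ²)]. The documents give neither spread, so I assume SD(duration) = 3 years and residual σ = 1 SDS:

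| Correlation ρ | Formula | Median in simulation |
|---|---|---|
| 0 | 2.179/(3 × 3.742) = 0.194 | 0.20 |
| −0.5 | 0.194/0.866 = 0.224 | 0.23 |
| −0.9 | 0.194/0.436 = 0.445 | 0.46 |

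Units are SDS per year. Strong negative correlation is plausible. Follow-up ends at Tanner Stage V or at age 16 (females) or 17 (males), so for a child treated throughout, duration is roughly exit age minus age at start.

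By the Fisher transformation, the partial correlation detectable with 80% power is tanh[(1.960 + 0.842)/√11] = 0.69 at N = 15, against 0.39 at N = 50.

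**The case against.** The strongest reply is that the plan already protects itself. A reader might infer that it commits to fitting a logistic regression to 15 patients. It does not: the model is conditional, the SAP amendment added the condition on patient numbers, and SAP 4.2 calls 15 patients too few for any comparison. Read together, the model will probably not be run. This stands, and it moves the weight of the point to what remains when the condition fails and to the missing thresholds.

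A reader might also infer that continuous SDS is discarded and that a general downward shift would go unseen. The text does not support that. Yearly summaries from the start of everolimus are unconditional, with a pre-treatment baseline, and individual graphs are drawn. For children who stay on treatment, years since start approximates exposure, so a progressive decline could show there. What is missing is narrower: an analysis across patients of SDS against their own duration.

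Third, the alternative is itself weak. With the assumed spreads and uncorrelated covariates, a linear model detects a slope of −0.3 SDS per year in about 80% of trials and −0.2 in about 50%. At a correlation of −0.5 these fall to about 69% and 40%, and at −0.9 to about 25% and 14%. A slope of −0.3 is also steep: 3 SDS over ten years. This stands too, and is why the proposal is for an estimate with an interval.

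Finally, the study is mainly descriptive and this step is exploratory. True, but a slope with an interval and a scatter plot suits a descriptive study better than a conditional logistic model.

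**Conclusion.** The point holds in a limited form. The only planned analyses relating individual exposure duration to growth use a dichotomised outcome for which 0.75 to 1.5 events are expected in 15 patients. They depend on two conditions without numbers, and SAP 4.2's conclusion about sample size is not carried into 3.8.1. The event counts and the ceiling of 7 in the smaller class need only the documents' N and rate. The separation, power and precision figures rest on the assumptions stated with them.

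The documents do not support saying that continuous SDS would answer the question where the cut outcome cannot. At N = 15 it gives an estimable, more efficient but imprecise slope. Nor is this a dose question: the model contains duration, with trough concentration only optional. The change is worth making because it is nearly free, but it concerns an exploratory step and leaves the main descriptive analysis of the primary endpoints untouched.

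**What to change.** In SAP 3.8.1:

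- Replace the logistic regression with a linear regression of continuous last height SDS, and separately BMI SDS, on total exposure duration. Change from the SAP 2.1.4 baseline may be the outcome instead. Run it whatever the abnormality rate, and label it exploratory.
- Adjust for baseline SDS where available, so that stature before treatment is not read as a treatment effect.
- Report the slope with and without age at start, since that covariate is likely to be strongly negatively correlated with duration.
- Give each slope with its 95% CI and a scatter plot of the 15 patients, and present it as an estimate without a test.
- Keep the below-5th-percentile rate as a descriptive endpoint with its exact interval.
- Give numeric thresholds for a sufficient number and a high rate wherever those conditions still govern an analysis, and record the change in SAP section 4.

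The cost is a few lines of SAP text and one simpler model, with no new data. The drawback to state in the SAP is low precision: a half-width of roughly 0.20 to 0.46 SDS per year under the assumed spreads.

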3.8.2 Tanner Stage

For CRAD001M2305 patients, all data described below will be pooled with the corresponding data from Study CRAD001M2301.

Tanner Stage will include two components for boys (testis and pubic hair) and two components for girls (breast development and pubic hair).

Percentage of patients who will have reached Tanner Stage V by age 16 (for females) or age 17 (for males) will be provided, side by side, on the FAS Puberty of the studies CRAD001M2305 and TOSCA, along with 95% confidence intervals.

If the number of CRAD001M2305 patients is sufficient and notably high abnormality, the relationship between the everolimus exposure and the Tanner Stage will be further explored as detailed below:

- The percentage of patients who will have reached Tanner Stage V by age 16 (for females) or age 17 (for males) will be described in the different subgroups defined by duration of everolimus exposure. These subgroups are described in the Section 3.12.
- The duration of exposure and the age at start of everolimus will be summarized using descriptive statistics in the subgroups of patients who will reach and who will not reach Tanner Stage V by age 16 (for females) or age 17 (for males).
- A logistic regression including the duration of exposure and the age at the start of everolimus as continuous covariates may also be used to further explore if needed the relationship between the everolimus exposure and the achievement of Tanner Stage V by age 16 (for females) or age 17 (for males). Additional covariates (e.g. time normalized C_{min}) might also be included in the model.

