**Secondary endpoints:**

- Safety assessments will consist of monitoring and recording adverse events, including serious adverse events. Safety will be assessed by the National Cancer Institute's (NCI) Common Toxicity Criteria for Adverse Events (CTCAE), version 3.0 ([//ctep.cancer.gov/protocolDevelopment/electronic\\_applications/docs/ctcae3.pdf](http://ctep.cancer.gov/protocolDevelopment/electronic_applications/docs/ctcae3.pdf)).
- Age at Tanner Stage II-V
- Age at start of menses (menarche) – for females
- Age at thelarche – for females
- Age at adrenarche – for males
- TAND Checklist - individual responses over time since the enrollment date
- Indirect comparison between CRAD001M2305 and CRAD001MIC03 will be performed on the following endpoints:
  - Percentage of patients who achieved Tanner Stage V at or before age of 16 (females) or 17 (males).
  - Height/BMI standard deviation score by year since baseline

Objectives and related endpoints are described in [Table 3-1](#) below.

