# 5 Population

## 5.1 Patient population

The target population is comprised of pediatric female and male patients who have previously participated in the study [CRAD001M2301] and have not, prior to enrollment into CRAD001M2305, reached age 16 for females, or age 17 for males. Additionally, these patients will not yet have achieved Tanner Stage V. Study treatment in study [CRAD001M2301] must have been completed within 6 months prior to enrollment into CRAD001M2305.

The investigator or designee must ensure that only patients who meet all inclusion are offered participation in the study. No additional exclusions can be applied by the investigator, in order that the study population will be representative of all eligible patients. All screening assessments must be completed and reviewed by the investigator (or designee) prior to starting study participation in CRAD001M2305.

All pediatric study patients and their parent(s) or legal guardian must be thoroughly informed about all aspects of the study, including the study visit schedule and required evaluations, and all regulatory requirements in order to ensure informed consent. The written informed consent must be obtained prior to performing any CRAD001M2305 study procedures. If the patient is unable to read, an impartial witness and/or the patient's parent or legal guardian must be present during the entire informed consent discussion. The following criteria apply to all patients enrolled into the study.

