### **7.1.3 Study completion**

Patients will meet the criteria for study completion upon demonstrating Tanner Stage V, or reaching age 16 (females) or age 17 (males), whichever comes first. Upon meeting the criteria for study completion, the patient should schedule an End of Study visit at the site. The End of Study visit cannot be completed via telephone contact.

Patients who discontinue commercial everolimus should continue study participation until meeting any of the aforementioned criteria for study completion. The discontinuation of everolimus will be recorded on the End of Treatment CRF page. Safety monitoring should be continued for at least 30 days following the last dose of everolimus.

Patients who complete the study, or discontinue the study early, should have the reason for exiting the study recorded on the Study Phase Completion Disposition CRF (SEC) page.

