2.3.1 Full Analysis Set

In order to describe data from the CRAD001M2305 patients and those from the TOSCA registry side by side, the following analysis sets will be used.

- The Full Analysis Set (FAS):
 - for CRAD001M2305, FAS will consist of all patients enrolled in the CRAD001M2305 study.
 - for TOSCA, FAS will consist of all patients enrolled in this TOSCA registry whose age at study entry was below 16 (for female) and 17 (for male) years and who never received an mTOR inhibitor throughout the registry follow-up period nor recorded as prior or ongoing treatment at the baseline visit.
- The Full Analysis Set for sexual development (FAS Puberty):
 - for CRAD001M2305, FAS Puberty will consist of the FAS patients defined above.
 - for TOSCA, FAS Puberty will consist of the FAS patients defined above but restricting from the patients to those aged between 9 to 17 years (for, females 9 to 16 years, males 9 to 17 years) at registry entry. The TOSCA registry is designed to collect Tanner Staging until 2017 (i.e. 4 to 6 years of follow-up). Thus it is considered adequate to select only TOSCA patients aged between 9 to 17 years old at the time of entry to the registry to allow for obtaining puberty data corresponding to the peri-pubertal time frame.

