3.1 General presentation of descriptive summaries

Qualitative data (e.g., gender, race, etc.) will be summarized by appropriate descriptive statistics (i.e. frequencies and percentages); a missing category will be included as applicable. Percentages will be calculated using the number of patients in the relevant population or subgroup as the denominator.

Quantitative data (e.g., age, body weight, etc.) will be summarized by appropriate descriptive statistics (i.e. mean, standard deviation, median, 25th and 75th percentiles, minimum, and maximum).

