3.8.4 Handling of missing values/censoring/discontinuations

All missing data will simply be described as missing until not specified on appropriate tables/listings in particular for patients who will not have reached Tanner Stage V or the age of 16 years (for females) or the age of 17 years (for males) at the end of the CRAD001M2305 study or at the end of the TOSCA registry using the FAS Puberty or Height, BMI analysis using the FAS population.

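### The primary Tanner Stage V percentage keeps patients of unknown status in its denominator, so the TOSCA column reads low and is not comparable with the M2305 column

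*SAP*

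**What the plan says.** **Endpoint.** SAP 3.8.2: "Percentage of patients who will have reached Tanner Stage V by age 16 (for females) or age 17 (for males) will be provided". The two studies stand next to each other on FAS Puberty, with 95% confidence intervals. The section states no denominator of its own.

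**Denominator.** SAP 3.1: "Percentages will be calculated using the number of patients in the relevant population or subgroup as the denominator". The same section adds a missing category where applicable.

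**Undetermined status.** SAP 3.8.4: "All missing data will simply be described as missing until not specified on appropriate tables/listings". It names in particular patients who have reached neither Stage V nor 16/17 when the study or registry ends. Protocol 10.4.2 says the same.

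**TOSCA follow-up.** SAP 2.3.1: "The TOSCA registry is designed to collect Tanner Staging until 2017 (i.e. 4 to 6 years of follow-up"). Entry ages are 9–16 (girls) and 9–17 (boys), with no condition on Tanner stage at entry.

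**M2305 follow-up.** Protocol 5.1: "Additionally, these patients will not yet have achieved Tanner Stage V". Protocol 7.1.3: "Patients will meet the criteria for study completion upon demonstrating Tanner Stage V, or reaching age 16 (females) or age 17 (males").

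**Related analysis.** SAP 3.9.2 plans Kaplan-Meier estimates of age at each Tanner stage, including V, on FAS Puberty, with proportions at given ages. SAP 3.8.2 does not refer to it.

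**The concern.** The M2305 column follows each patient until the outcome is settled, unless the patient leaves early. The TOSCA column does not: a child who enters at 9 is last staged at 13 to 15. If that child would have reached Stage V by 16/17, the crude percentage never credits it, yet the child stays in the denominator. TOSCA's figure then falls short of its own true attainment by an amount that does not shrink with more patients.

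This matters because TOSCA is there as the untreated TSC reference. SAP section 1 says the side-by-side display should help separate the effect of TSC from that of everolimus. SAP 4.2 calls the indirect comparison not meaningful, so readers will rely more on this display. A reference that understates attainment could make M2305 look better than it should. The limited TOSCA follow-up is acknowledged in SAP 3.9.3 for the indirect comparison, but not beside this percentage.

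**Working it through.** **1. The plan's own figures.** No expected Stage V percentage is given. The only numbers for rates are the exact intervals. Clopper-Pearson reproduces them: 4/50 gives (0.022, 0.192) against the stated (0.02, 0.19); 1/15 gives (0.002, 0.319) against (0.00, 0.32); 12/15 gives (0.519, 0.957) against (0.52, 0.96).

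**2. Share of TOSCA whose staging stops before the cut-off.** Let c be 16 (girls) or 17 (boys) and F the years of follow-up. With entry ages uniform from 9 to c (an assumption), the share is (c − F − 9)/(c − 9).

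| F | Girls | Boys |
|---|---|---|
| 4 | 3/7 = 43% | 4/8 = 50% |
| 5 | 2/7 = 29% | 3/8 = 38% |
| 6 | 1/7 = 14% | 2/8 = 25% |

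These shares are ceilings on the shortfall, because some of these patients reach Stage V while still observed.

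**3. Size of the TOSCA shortfall.** Assumptions, none given in the documents: age at Stage V, T, is normal with SD 1.2; entry age E is uniform as above; F is uniform on 4–6 years; there is no dropout; ages at Stage V are observed exactly.

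- True attainment = P(T ≤ c) = Φ((c − mean)/1.2).
- TOSCA crude = P(T ≤ min(c, E + F)), averaged over E and F.
- M2305 crude = P(T ≤ c given T > entry age), with entry uniform from 5 or 9 up to c − 0.25.

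| Sex, mean T | True % | TOSCA crude % | Shortfall | M2305 crude % (entry from 5 / 9) |
|---|---|---|---|---|
| Girls 14.0 | 95.2 | 89.3 | 5.9 | 94.3 / 93.5 |
| Girls 14.5 | 89.4 | 81.6 | 7.8 | 87.9 / 86.8 |
| Girls 15.0 | 79.8 | 70.7 | 9.1 | 77.8 / 76.5 |
| Boys 15.0 | 95.2 | 82.6 | 12.6 | 94.4 / 93.8 |
| Boys 15.5 | 89.4 | 74.3 | 15.1 | 88.1 / 87.2 |
| Boys 16.0 | 79.8 | 63.6 | 16.2 | 78.0 / 77.0 |

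One year below the lowest mean in the table (girls 13, boys 14; true 99.4%), TOSCA reads 97.1% for girls (2.3 low) and 93.0% for boys (6.4 low). The M2305 column is about 1–3 points below the truth in the table because its entry rule removes early maturers.

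**4. Net difference with no true effect.** M2305 minus TOSCA, same T in both, equal dropout in both:

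| Dropout per year | Difference (points) |
|---|---|
| 0% | +4 to +14 |
| 2.5% | −2 to +10 |
| 5% | −7 to +7 |

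M2305 leavers also stay in their denominator, and M2305 patients can be followed for longer, so dropout costs that column more.

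**5. Candidate remedies.**

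- *Drop the missing patients:* at a true 79.8%, TOSCA becomes 83.0% (girls) and 83.4% (boys), because the outcome helps decide who stays in.
- *Keep only patients whose entry age plus planned follow-up reaches c, whatever their outcome:* this recovers the truth without dropout, using about 71% of girls and 62% of boys. With 5% yearly dropout it is still 4–5 points low.
- *Plain Kaplan-Meier at c:* with exact ages, TOSCA agrees with the truth to within 0.1 point in every cell, with or without dropout. M2305 still reads about 1–3 points low (up to 3.7 with 5% yearly dropout). Letting patients enter the risk set at enrolment age removes this to within 0.2 point.

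**The case against.** The strongest reply is that the plan already deals with most of this. The patients are labelled missing, not failures; a missing row is foreseen; and Kaplan-Meier for the same milestone on the same set is planned and handles short follow-up. No test is planned (SAP 2.4.2.1), and SAP 4.2 says 15 patients are too few for any comparison: 12/15 has an interval 44 points wide.

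Much of that stands and limits the point. A reader might infer that the plan classes these patients as not reached; it does not. But a missing row leaves the denominator unchanged, so the printed percentage and its interval are the same as if it did. The Kaplan-Meier analysis is secondary, is not linked to the primary percentage, and states no delayed entry for M2305.

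Three stronger readings are also tempting and are not supported:

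- *The display hides a real delay under everolimus.* This is possible but not shown, since the net bias can take either sign.
- *Stage V at entry makes TOSCA read low.* It does not: such patients enter before 16/17 and correctly count as reached. The M2305 exclusion lowers M2305 instead.
- *Visit timing adds a large, known further gap.* Protocol 7.1.3 says "Upon meeting the criteria for study completion, the patient should schedule an End of Study visit at the site", but the visible text does not confirm Tanner staging at that visit and gives no TOSCA Tanner interval. This supports asking for a common dating rule, not quoting a size.

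**Conclusion.** The point holds as one of interpretation and should be fixed. Read together, SAP 3.1, 3.8.2 and 3.8.4 give a TOSCA percentage below that registry's true attainment, set beside an M2305 percentage with different follow-up and a different entry condition. The size (about 6–9 points for girls and 13–16 for boys, or 2 and 6 with earlier maturation) rests on assumed entry ages, Stage V ages and complete follow-up. The existence of a shortfall needs only that some TOSCA patients reach Stage V by 16/17 after their staging has stopped. With about 15 M2305 patients, sampling error dominates that column, and no formal conclusion is at risk.

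**What to change.** In SAP 3.8.2, make the side-by-side figure the proportion at Stage V by 16 (girls) and 17 (boys), per sex, from the Kaplan-Meier analysis in SAP 3.9.2 read at those ages. Specify:

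- censoring at the last Tanner assessment;
- entry to the risk set at enrolment age for M2305;
- one rule for dating Stage V in both studies, covering Stage V first seen at a closing visit and Stage V already present at the first TOSCA assessment.

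Print beside it, per study and sex, the counts reached, not reached at 16/17, and unknown. With so few M2305 patients, these counts will be the most readable part of that column.

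If the crude percentage is kept, limit its denominator to patients whose entry age plus planned follow-up reaches 16/17, whatever their outcome, and report that n. Do not simply drop the missing patients. Interval censoring is optional.

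Cost: SAP wording and minor re-programming before final database lock, with no new data. The restricted crude figure uses fewer TOSCA patients and does not correct for dropout.
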